11.1.3 Abnormal hematologic and chemical values

Abnormal hematologic and chemical values, the apogee or nadir (whichever is appropriate) will be reported per course on the case report form.

11.1.4 Attribution of AEs

All events will be collected for the purpose of grading, and determining attribution to study drugs by the PI using the following scale:

- Unrelated: The AE is clearly NOT related to the intervention.
- Unlikely: The AE is doubtfully related to the intervention.
- Possible: The AE may be related to the intervention.
- Probable: The AE is likely related to the intervention.
- Definite: The AE is clearly related to the intervention.

11.1.5 Documentation of grade 3 and greater non-hematologic adverse events

All grade 3 and greater non-hematological events that are felt to be related to protocol treatment drugs will be documented on the toxicity log and entered into the case report form. The toxicity log and case report form data must reflect the relationship to the drug the event is felt to be related to.

11.1.6 Serious Adverse Event Reporting (SAE)

An adverse event or suspected adverse reaction is considered “serious” if, in the view of either the investigator or the sponsor, it results in any of the following outcomes:

- Death
- A life-threatening adverse drug experience; this is defined as any adverse experience that places the patient, in view of the initial reporter, at immediate risk of death from the adverse experience, as it occurred. It does not include an adverse experience that, had it occurred in a more severe form, might have caused death.
- Inpatient hospitalization or prolongation of existing hospitalization.
- A persistent or significant incapacity or substantial disruption of the ability to conduct normal life functions.
- A congenital anomaly/birth defect.

11.1.7 Serious adverse reaction (SAR)

An SAE where a causal relationship between a medicinal product and the SAE is at least a reasonable possibility, i.e., the relationship cannot be ruled out.

11.1.8 Suspected Unexpected Serious Adverse Reaction (SUSAR)

An SAR, the nature or severity of which is not consistent with the applicable product information i.e. Investigator's Brochure for an unauthorized medicinal product or summary of product characteristics for an authorized product).

11.2 "Serious Adverse Event Reporting (SAE) for M. D. Anderson-Sponsored IND Protocols"

- All life-threatening or fatal events, that are unexpected, and related to the study drug, must have a written report submitted within 24 hours (next working day) of knowledge of the event to the Safety Project Manager in the IND Office.
- Unless otherwise noted, the electronic SAE application (eSAE) will be utilized for safety reporting to the IND Office and MDACC IRB.
- Serious adverse events will be captured from the time of the first protocol-specific intervention, until 100 days after the last dose of drug, unless the participant withdraws consent. Serious adverse events must be followed until clinical recovery is complete and laboratory tests have returned to baseline, progression of the event has stabilized, or there has been acceptable resolution of the event.
- Additionally, any serious adverse events that occur after the 100 day time period that are related to the study treatment must be reported to the IND Office. This may include the development of a secondary malignancy.

11.3 Reporting to FDA

- Serious adverse events will be forwarded to FDA by the IND Sponsor (Safety Project Manager IND Office) according to 21 CFR 312.32.

Important medical events that may not result in death, be life-threatening, or require hospitalization may be considered a serious adverse drug experience when, based upon appropriate medical judgment, they may jeopardize the patient or subject and may require medical or surgical intervention to prevent one of the outcomes listed in this definition. Examples of such medical events include allergic bronchospasm requiring intensive treatment in an emergency room or at home, blood dyscrasias or convulsions that do not result in inpatient hospitalization, or the development of drug dependency or drug abuse (21 CFR 312.32). Pregnancy, drug overdose, and secondary malignancy will be handled as SAE.

- Important medical events as defined above, may also be considered serious adverse events. Any important medical event can and should be reported as an SAE if deemed appropriate by the Principal Investigator or the IND Sponsor, IND Office.
- All events occurring during the conduct of a protocol and meeting the definition of a SAE must be reported to the IRB in accordance with the timeframes and procedures outlined in "The

University of Texas M. D. Anderson Cancer Center Institutional Review Board Policy for Investigators on Reporting Unanticipated Adverse Events for Drugs and Devices". Unless stated otherwise in the protocol, all SAEs, expected or unexpected, must be reported to the IND Office, regardless of attribution (within 5 working days of knowledge of the event).

It is the responsibility of the PI and the research team to ensure serious adverse events are reported according to the Code of Federal Regulations, Good Clinical Practices, the protocol guidelines, the sponsor's guidelines, and Institutional Review Board policy.

11.4 Investigator Communication with Amgen

- Suspected unexpected serious adverse reactions (SUSARs). When PI/Research staff receives a SUSAR, it shall transmit the final report of that event to Amgen within **twenty four (24) hours** of submitting that report to the applicable regulatory authority.
- Any pregnancy occurring during the study must be reported to Amgen within 10 days.
- SAEs will be reported to Amgen as a cumulative report, every 6 months.
- All adverse events recorded during the study will be forwarded to Amgen at the completion of the study for reconciliation. However, expedited reporting is not required for AEs not classified as serious.
- Investigational pharmacy will communicate with Amgen regarding how expired on unused drug will be handled.

All SAEs and SUSARs should be reported via confirmed facsimile (fax) transmission, or scanned and reported via electronic mail to:

[contact] (toll-free, US)

[contact] (toll) OR

E-mail: [contact].

11.5 Investigator Communication with BMS

- All Serious Adverse Events (SAEs) that occur following the subject's written consent to participate in the study through 100 days of discontinuation of dosing must be reported to BMS

Worldwide Safety, whether related or not related to study drug. If applicable, SAEs must be collected that relate to any later protocol-specified procedure (eg, a follow-up skin biopsy).

- Following the subject's written consent to participate in the study, all SAEs, whether related or not related to study drug, are collected, including those thought to be associated with protocol-specified procedures. The investigator should report any SAE occurring after these aforementioned time periods, which is believed to be related to study drug or protocol-specified procedure.
- An SAE report should be completed for any event where doubt exists regarding its seriousness;
- If the investigator believes that an SAE is not related to study drug, but is potentially related to the conditions of the study (such as withdrawal of previous therapy or a complication of a study procedure), the relationship should be specified in the narrative section of the SAE Report Form.
- Institutional eSAE form will be used to submit SAE data to BMS. Note: Please include the BMS Protocol number on the SAE form or on the cover sheet with the SAE form transmission.
- The Sponsor will reconcile the clinical database AE cases (**case level only**) transmitted to BMS Global Pharmacovigilance ([contact]).
 - The Investigator will request from BMS GPV&E, [contact] the SAE reconciliation report and include the BMS protocol number every 3 months and prior to data base lock or final data summary
 - GPV&E will send the investigator the report to verify and confirm all SAEs have been transmitted to BMS GPV&E.
 - The data elements listed on the GPV&E reconciliation report will be used for case identification purposes. If the Investigator determines a case was not transmitted to BMS GPV&E, the case should be sent immediately to BMS ([contact]).
- In addition to the Sponsor Investigator's responsibility to report events to their local HA, suspected serious adverse reactions (whether expected or unexpected) shall be reported by BMS to the relevant competent health authorities in all concerned countries according to local regulations (either as expedited and/or in aggregate reports).
- In accordance with local regulations, BMS will notify sponsor investigators of all reported SAEs that are suspected (related to the investigational product) and unexpected (ie, not previously described in the IB). An event meeting these criteria is termed a Suspected, Unexpected Serious

Adverse Reaction (SUSAR). Sponsor investigator notification of these events will be in the form of either a SUSAR Report or a Semi-Annual SUSAR Report.

- ✓ Other important findings which may be reported by BMS as an Expedited Safety Report (ESR) include: increased frequency of a clinically significant expected SAE, an SAE considered associated with study procedures that could modify the conduct of the study, lack of efficacy that poses significant hazard to study subjects, clinically significant safety finding from a nonclinical (eg, animal) study, important safety recommendations from a study data monitoring committee, or sponsor or BMS decision to end or temporarily halt a clinical study for safety reasons.
- ✓ Upon receiving an ESR from BMS, the investigator must review and retain the ESR with the IB. Where required by local regulations or when there is a central IRB/IEC for the study, the sponsor will submit the ESR to the appropriate IRB/IEC. The investigator and IRB/IEC will determine if the informed consent requires revision. The investigator should also comply with the IRB/IEC procedures for reporting any other safety information.

SAEs, whether related or not related to study drug, and pregnancies must be reported to BMS within 24 hours \ 1 Business Day of becoming aware of the event. SAEs must be recorded on either CIOMS, MedWatch, or approved site SAE form.

Pregnancies must be reported and submitted to BMS. BMS will perform due diligence follow-up using the BMS Pregnancy Form which the investigator must complete.

SAE Email Address: [contact]

SAE [contact]

If only limited information is initially available, follow-up reports are required. (Note: Follow-up SAE reports should include the same investigator term(s) initially reported.)

If an ongoing SAE changes in its intensity or relationship to study drug or if new information becomes available, a follow-up SAE report should be sent within 24 hours \ 1 Business Day to BMS using the same procedure used for transmitting the initial SAE report.

All SAEs should be followed to resolution or stabilization.

The causal relationship to study drug is determined by a physician and should be used to assess all adverse events (AE). The causal relationship can be one of the following:

Related: There is a reasonable causal relationship between study drug administration and the AE.

Not related: There is not a reasonable causal relationship between study drug administration and the AE.

The term "reasonable causal relationship" means there is evidence to suggest a causal relationship.

Adverse events can be spontaneously reported or elicited during open-ended questioning, examination, or evaluation of a subject. (In order to prevent reporting bias, subjects should not be questioned regarding the specific occurrence of one or more AEs.)

NONSERIOUS ADVERSE EVENT

- Non-serious Adverse Events (AE) are to be provided to BMS in aggregate via interim or final study reports as specified in the agreement or, if a regulatory requirement [eg, IND US trial] as part of an annual reporting requirement.
- Non-serious AE information should also be collected from following the subject's written consent to participate in the study.

Non-serious Adverse Event Collection and Reporting

The collection of non-serious AE information should begin following the subject's written consent to participate in the study. All non-serious adverse events (not only those deemed to be treatment-related) should be collected continuously during the treatment period and for a minimum of 100 days following the last dose of study treatment.

Non-serious AEs should be followed to resolution or stabilization, or reported as SAEs if they become serious. Follow-up is also required for non-serious AEs that cause interruption or discontinuation of study drug and for those present at the end of study treatment as appropriate.

Laboratory Test Abnormalities

All laboratory test results captured as part of the study should be recorded following institutional procedures. Test results that constitute SAEs should be documented and reported to BMS as such.

The following laboratory abnormalities should be documented and reported appropriately:

- any laboratory test result that is clinically significant or meets the definition of an SAE
- any laboratory abnormality that required the participant to have study drug discontinued or interrupted
- any laboratory abnormality that required the subject to receive specific corrective therapy.

It is expected that wherever possible, the clinical rather than laboratory term would be used by the reporting investigator (eg, anemia versus low hemoglobin value).

12.0 CRITERIA FOR REMOVAL FROM STUDY.

Criteria for removal from study include, but are not restricted to, the following:

- Clinically significant progressive disease.
- Recurrent non-compliance by the patient with protocol requirements.
- Patient's request to be removed from the study.
- Investigator's decision that a subject does not benefit from treatment anymore, e.g., non-response or development of progressive disease
- Transition to an alternative therapy, including allogeneic stem cell transplantation.
- Permanent cessation of nivolumab **and** blinatumomab: if a patient permanently discontinues either nivolumab or blinatumomab (but not both) due to adverse events, they may remain on study, if they continue to derive treatment benefit and benefit outweighs risk, in the opinion of the investigator. Patients who permanently discontinue both nivolumab and blinatumomab due to adverse events will be removed from the study.
- Permanent discontinuation of ibrutinib for any reason will not be an indication to remove a patient from study, if, in the opinion of the investigator, the patient is deriving benefit from treatment and it is safe to continue the other agent(s).

13.0 CORRELATIVE STUDIES

All correlative studies are optional and failure to collect these studies at any of the specified time-points is not a protocol deviation. Patients will consent separately to having these studies taken.

13.1 Immunologic analyses

The purpose of these analyses is to determine pre-treatment immunologic parameters predictive of response to blinatumomab treatment and to evaluate treatment-induced immunologic changes within the blood and tumor tissue during treatment and their correlation with response:

13.1.1 Studies on tumor tissue

Patients will have surgical excisional biopsy or interventional radiology-guided core biopsies performed at baseline if required for diagnostic purposes. If patients consent to a separate IRB-approved protocol (PA15-0965), excess tumor tissue will be cryopreserved and used for exploratory immunohistochemical characterization of tumor infiltrating lymphocyte (TIL) populations, including expression of immune checkpoint molecules (PD1 and PDL1). In addition, tissue will be cryopreserved for later genomic investigation (see section 13.2, below)

13.1.2 Studies on peripheral blood T-cell population

In addition, if patients consent, circulating T-cell numbers and function will be analyzed at the following time points: i) baseline; ii) 24-48 hours after initiation of cycle 1; iii) 1 week after initiation of cycle 1; iv) 4 weeks after initiation of cycle 1; v) prior to initiation of cycle 5; vi) at the completion of cycle 2. This comprehensive analysis will include both phenotypic and functional characterization of T-cells, as well as the expression levels of immune checkpoint molecules. We hypothesize that T-cell numbers and function will be predictive of response to blinatumomab and that up-regulation of PD1 on T-cells will be a potential resistance mechanism. This testing will be performed on protocol PA16-0360.

13.2 Tumor banking.

Patient tumor tissue, DNA, RNA and plasma will be stored pre-treatment and at relapse on a separate IRB-approved research protocols (PA15-0965). This will be optional and patients will sign separate consent forms for this. At a later date, this tissue may be used in genomic and proteomic studies to determine drivers of disease biology and resistance mechanisms to therapy.

13.3 Evaluation of plasma circulating tumor DNA (ctDNA)

If patients consent, peripheral blood samples will be collected, processed and banked at baseline, 1st and 2nd response assessments, 12 and 24 months and at the time of relapse. We will bank saliva from patients at baseline; sequencing from saliva will serve as a normal control. In patients where there is a clinical need to perform a lymph node biopsy for diagnostic purposes (eg. suspicion of Richter Transformation), we will use leftover tissue for sequencing. Targeted next-generation sequencing will be performed on ctDNA and compared to bone marrow, peripheral blood mononuclear cells and lymph node tissue, where available. At disease progression, we will perform whole exome and low coverage whole genome sequencing, where appropriate, from the cellular component of peripheral blood, plasma and/or bone marrow at baseline and relapse and from nodal tissue where available, to identify mutations and copy number alterations which have emerged during therapy and may be responsible for resistance. This testing will be performed at Peter MacCallum Cancer Centre in Melbourne, Australia. If new, somatic mutations are identified at progression, targeted deep sequencing and/or digital PCR testing for these mutations will be performed from stored, serial plasma samples to identify and quantitate their presence in plasma over time. This testing will be performed on protocol PA16-0919 as an optional procedure.

14.0. STATISTICAL CONSIDERATIONS

The cohort of 9 patients already treated demonstrates the feasibility and safety of blinatumomab as a single agent for the treatment of RT. The overall toxicity profile of blinatumomab in RT was very favorable and this cohort of patients can be used as a “safety cohort,” prior to proceeding with a phase II study evaluating the combination with ibrutinib + nivolumab. As discussed above, the combination of ibrutinib and nivolumab was also very well tolerated.

We have completed a phase II study of ibrutinib + nivolumab, and achieved an ORR of 43%. This will serve as our “base case” estimation of the response rate that we would see with the combination of ibrutinib + nivolumab. If blinatumomab (ORR 1/8 = 12.5%) provides additive benefit only, this will result in an ORR of 50-55% with the combination of ibrutinib + nivolumab and blinatumomab. However, we expect synergy between the two regimens. We have therefore designed our statistical analysis around achieving an ORR of approximately 60%, which would suggest some synergy

between the two regimens. Higher response rates would suggest a greater degree of synergy between blinatumomab and ibrutinib + nivolumab, which we hope to achieve.

We propose to enroll an additional 21 patients, with the goal of evaluating the efficacy and safety of the proposed combination therapy. A sample size of 21 patients ensures that, if the trial is not terminated early, a posterior 90% credibility interval for overall response rate will have width of 0.33, under the assumption of a 60% of overall response rate (13/21 responses) and beta prior as described below. Under this scenario, the lower boundary of the 90% credibility interval matches the 43% ORR that was seen with ibrutinib + nivolumab therapy.

The primary outcome will be overall response (ORR), assessed after completion of 2 courses of blinatumomab.

We will utilize a Bayesian trial design to enable simultaneous monitoring of efficacy and toxicity using the approach of Thall, Simon, and Estey (1995, 1996). After an initial 6 patient safety cohort, subsequent patients will be enrolled in cohorts of size 3.

The existing trial of blinatumomab as a single agent assumes that a toxicity rate greater than 31% would be excessive. Since we propose combining blinatumomab with two additional agents, we aim to achieve a higher ORR, and allow for acceptable toxicity no higher than 40%. For the purposes of toxicity monitoring, toxicity will be defined as follows: grade 4-5 neurotoxicity or CRS; grade 3 neurotoxicity or CRS that fails to resolve within 1 week or recurs at grade ≥ 3 severity on re-challenge; grade 3-5 therapy-related immune-related toxicity at least possibly related to nivolumab.

For the Bayesian design, the following parameter settings will be used:

- For the standard treatment response and toxicity rates, constant rates of 0.4 are assumed.
- For the response and toxicity rates under the proposed treatment, a beta(0.8, 1.2) prior is assumed for each rate, which has the same mean as the rates under the standard treatment, and an effective sample size of 2.
- The maximum number of patients if no early stopping is applied will be 21, and a minimum of 6 patients will be treated before stopping.
- The planned cohort size is 3.

- The trial will be stopped early based on response if the posterior probability that the response rate of the experimental treatment is less than the current standard rate is greater than 0.9.
- The trial will be stopped early based on toxicity if the posterior probability that the toxicity rate of the experimental treatment is greater than the current standard rate is greater than 0.8.
- Toxicity will be monitored continuously for the first year of treatment.

Response Stopping Boundaries

# Patients (in complete cohorts of 3) (inclusive)	Stop the trial if there are this many responses total:

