	# Toxicities (inclusive)
3	Never stop with this many patients
6	4-6
9	5-9
12	7-12
15	8-15
18	10-18
21	Always stop with this many patients

Summary of operating characteristics

The operating characteristics are summarized in the table below. The probabilities of stopping the trial early are exact calculations from MultcLean Desktop under the assumption that response is independent of toxicity.

True Toxicity Rate	True OR Rate	Prob(stop the trial early)	Avg # patients enrolled (25 th – 75 th percentile)
0.2	0.6	0.04	20.5 (21 – 21)
	0.5	0.07	20.1 (21 – 21)
	0.4	0.19	19.0 (21 – 21)
	0.3	0.45	16.4 (12 – 21)
0.3	0.6	0.14	19.2 (21 – 21)
	0.5	0.17	18.8 (21 – 21)
	0.4	0.28	17.8 (15 – 21)
	0.3	0.51	15.5 (9 – 21)
0.4	0.6	0.36	16.4 (9 – 21)
	0.5	0.39	16.2 (9 – 21)
	0.4	0.46	15.4 (9 – 21)
	0.3	0.63	13.6 (6 – 21)
0.5	0.6	0.64	12.9 (6 – 21)
	0.5	0.66	12.7 (6 – 15)
	0.4	0.70	12.2 (6 – 21)
	0.3	0.79	11.1 (6 – 15)

Analysis Plan

Summary statistics will be provided for continuous variables. Frequency tables will be used to summarize categorical variables. Logistic regression will be utilized to assess the effect of patient prognostic factors on the response rate and the toxicity rate. The distribution of time-to-event endpoints will be estimated using the method of Kaplan and Meier. Cox proportional hazard regression will be employed for multivariate analysis on time-to-event outcomes.

An Efficacy/Safety Summary will be submitted to the IND Office Medical Monitor, after the first 6 evaluable patients complete 8 weeks of study treatment, and every 3 evaluable patients thereafter. Toxicity information of previously submitted patients will be updated during every submission.

Trial Conduct

Conducting a trial designed by this method does not require software since the stopping conditions have been tabulated before the trial begins.

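### The toxicity stopping boundary counts a closed list of events, so a treatment-related death from infection, bleeding or tumor lysis adds nothing while a grade 3 nivolumab immune event adds one

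*Combined protocol and SAP*

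**What the plan says.** Section 14.0 gives three kinds of event for toxicity monitoring. The first two are in this wording: "toxicity will be defined as follows: grade 4-5 neurotoxicity or CRS; grade 3 neurotoxicity or CRS that fails to resolve within 1 week", extended to grade 3 events that recur at grade 3 or above on re-challenge. The third is "grade 3-5 therapy-related immune-related toxicity at least possibly related to nivolumab". The list has no open-ended wording, no item for related deaths in general and no item for ibrutinib toxicity.

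The boundary built on this event stops the trial at 4/6, 5/9, 7/12, 8/15 or 10/18 patients with toxicity. On timing, the section says: "Toxicity will be monitored continuously for the first year of treatment". The Trial Conduct paragraph treats the tabulated counts as the working rule: "Conducting a trial designed by this method does not require software since the stopping conditions have been tabulated before the trial begins".

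Other routes carry safety information:

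- Analysis Plan: "An Efficacy/Safety Summary will be submitted to the IND Office Medical Monitor, after the first 6 evaluable patients complete 8 weeks of study treatment"; later summaries follow each further group of 3 such patients.
- Section 11.2: "All life-threatening or fatal events, that are unexpected, and related to the study drug, must have a written report submitted within 24 hours".
- Section 11.3: "all SAEs, expected or unexpected, must be reported to the IND Office, regardless of attribution", within 5 working days.
- Section 11.5: "SAEs, whether related or not related to study drug, and pregnancies must be reported to BMS within 24 hours" or one business day.

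**The concern.** The protocol names the omitted outcomes as fatal risks of its own drugs: infection (Sections 5.1.2.5 and 5.3.5.5), tumor lysis (5.1.2.4) and bleeding, including intracranial bleeding (5.3.5.1). In the blinatumomab study summarized in Section 2.2.1, all three treatment-related grade 5 events were infections. Section 6.1 assigns neurotoxicity grading to Appendix E, and Appendix E excludes intracranial hemorrhage from the scale.

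The count therefore ranks outcomes the wrong way round. A grade 3 immune event moves the trial toward stopping and a related septic death does not. The gap is limited to related deaths outside the listed classes: fatal CRS, fatal neurotoxicity and deaths judged to be nivolumab immune-related already count.

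**Working it through.** **Inputs (Section 14.0).** Prior beta(0.8, 1.2) for each rate; standard rates 0.4; toxicity cutoff 0.8; response cutoff 0.9; looks at 6, 9, 12, 15 and 18 patients; maximum 21.

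**1. Reproducing the plan.** With x events in n patients:

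- toxicity bound: smallest x with P(Beta(0.8 + x, 1.2 + n − x) > 0.4) > 0.8, which gives 4, 5, 7, 8, 10;
- response bound: largest x with P(Beta(0.8 + x, 1.2 + n − x) < 0.4) > 0.9, which gives 0, 1, 2, 3, 4.

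Both match the printed tables. An exact recursion over the five looks, with toxicity and response independent, matches all 16 printed early-stopping probabilities to rounding. For example, at a true response rate (ORR) of 0.6 it gives 0.0375, 0.1431 and 0.362 for true toxicity 0.2, 0.3 and 0.4, against 0.04, 0.14 and 0.36 printed. The design is correctly calculated for the event as defined.

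**2. What the definition does.** Take the first 6 patients.

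- Four related deaths from sepsis, bleeding or tumor lysis and no listed event: count 0/6, P(toxicity > 0.4) = 0.017, no toxicity stop.
- Four grade 3 nivolumab immune events: count 4/6, P = 0.875, stop.

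In the first case the response rule stops only at 0/6 responses. One response among the other two patients is enough for the trial to continue under both rules.

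**3. Effect on early stopping.** The documents give no related-death rate for this regimen, so the rates are assumptions. The only figure is 3/189 = 1.6% (exact 95% CI 0.3% to 4.6%), for one drug in another disease; 10% is a stress case. Model per patient: listed toxicity with probability t; an unlisted related death with probability d, separate from listed toxicity and scored as a non-response; ORR 0.6 in the rest.

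| Listed toxicity t | Deaths d | Deaths uncounted | Deaths counted | Difference (points) |
|---|---|---|---|---|
| 0.20 | 3/189 | 0.039 | 0.049 | 1.0 |
| 0.20 | 2% | 0.040 | 0.052 | 1.2 |
| 0.20 | 5% | 0.043 | 0.082 | 3.9 |
| 0.20 | 10% | 0.053 | 0.154 | 10.1 |
| 0.30 | 3/189 | 0.145 | 0.172 | 2.7 |
| 0.30 | 2% | 0.145 | 0.179 | 3.4 |
| 0.30 | 5% | 0.149 | 0.243 | 9.4 |
| 0.30 | 10% | 0.157 | 0.369 | 21.2 |

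At t = 0.10 and d = 2% the figures are 0.0126 and 0.0145. If deaths occur independently of listed toxicity the gain is smaller: at 3/189, 0.039 to 0.047 (t = 0.20) and 0.145 to 0.163 (t = 0.30).

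The chance of at least one such death in 21 patients, 1 − (1 − d)^21, is 29%, 35%, 66% and 89% at d = 3/189, 2%, 5% and 10%.

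**4. How far the response rule compensates** (t = 0.30, d = 10%):

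| ORR | No deaths | Deaths uncounted | Gain from response rule (points) | Deaths counted |
|---|---|---|---|---|
| 0.60 | 0.143 | 0.157 | 1.4 | 0.369 |
| 0.50 | 0.174 | 0.215 | 4.1 | 0.407 |
| 0.43 | 0.235 | 0.303 | 6.8 | 0.468 |
| 0.40 | 0.278 | 0.357 | 7.9 | 0.507 |

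The backstop is weakest when the regimen is active. It cannot register a death after a response, although toxicity is followed for a year.

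**5. Limit of the remedy.** Under a 40% rule, related deaths alone at 3/6, 4/9 or 6/12 give P = 0.66, 0.58 and 0.74, all below 0.8. With no other toxicity and 10% deaths, early stopping is 0.024 uncounted and 0.026 counted.

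**The case against.** Monitoring a targeted event is a legitimate design choice. The list follows the signature toxicities of blinatumomab and nivolumab, and Section 6.1.4 gives a reason to watch their interaction. The plan does not contradict itself, and its boundaries are right for its event. The Trial Conduct paragraph does not say that the tables are the only grounds for stopping. SAE reports and Medical Monitor summaries put these deaths before people who can halt the trial. At the documented rate the change is about 1 to 3 points, and the largest figure needs a death rate more than twice the upper confidence limit of 4.6%. A cluster of deaths alone would still rarely cross a 40% boundary, so judgement remains the main safeguard.

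Most of this stands, and it limits the size of the point. It does not remove it. The plan chose a numeric rule for toxicity, and targeting explains the choice of non-fatal items better than the omission of related deaths in a triplet that includes ibrutinib.

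Three smaller points also have some force:

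- Section 6.1.1 acts on CTCAE-graded CNS events, so the exclusion of intracranial hemorrhage rests on reading the definition through Appendix E, as Section 6.1 directs.
- Scoring missing responses as non-responses is written only for CLL (Section 10.2), so the response backstop is itself an assumption.
- Whether an early death counts as an evaluable patient is a separate question that the plan should also settle.

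**Conclusion.** The concern holds. As written, a related death from infection, bleeding or tumor lysis has no weight in the toxicity boundary, and no other rule gives it a numeric trigger. This is a gap in the event definition, not a calculation error.

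Its practical size depends on assumed death rates. At ORR 0.6 and 3/189 deaths, counting them adds about 1 point of early stopping at 20% listed toxicity and about 3 points at 30%. The gain is negligible when other toxicity is rare. The case rests mainly on the coherence of the definition. The change should be made because it is cheap and the omitted outcome is the most serious one.

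**What to change.** Extend the Section 14.0 definition with one clause: *or any grade 5 event at least possibly related to any study drug*, counted once per patient. The sponsor should confirm, with a brief justification, that 40% is still the right limit for the wider event. Any separate limit on deaths is the sponsor's choice.

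The prior, cutoffs, boundaries and operating-characteristics table stay arithmetically valid, with the toxicity rate now referring to the wider event. No new data are needed: Section 11.1.2 already records all SAEs and Section 11.1.4 has the PI grade attribution.

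The cost is more early stopping when related deaths occur, by the amounts in the first table above. Attribution of infection deaths may also be uncertain in a disease where Section 2.1 reports median survival under one year in most series.
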